6.1.1. Neratinib Dose Adjustment

Neratinib dose adjustment and/or discontinuation and/or management of toxicity should be performed according to [Appendix 2](#) and [Section 10.1](#).

Recommended dose reductions for the -1 and -2 dose levels of neratinib are listed in [Table 3](#).

Table 3: Dose Reduction Levels for Neratinib-Related Toxicity

Dose Level	Neratinib
Recommended Starting Dose	240 mg
First dose reduction	200 mg
Second dose reduction	160 mg
Third dose reduction	120 mg

mg = milligrams

If doses of neratinib are held, study procedures for that cycle will proceed on schedule as planned, without any delay. Missed dose(s) of neratinib (i.e., any dose that is not administered within the protocol-defined administration window) will not be made up. **Note: Patients should take one dose per calendar day.** The dose adjustment guidelines represent the minimum set of measures the Investigator must follow. However, additional measures may be taken, as necessary, for certain patients per the Investigator's medical judgment. All dose modifications/adjustments should be documented in the patient's source file.

Once the neratinib dose has been reduced for a patient, all subsequent cycles must be administered at that dose, unless further dose reduction is required. Dose re-escalation will only be permitted if explicitly approved in advance by the Sponsor. Evidence of this approval must be contained within the patient's source file.

Patients must discontinue the investigational product if a criterion for withdrawal is met (see [Section 10.1](#)).

Reintroduction of the discontinued investigational product at a later time during the active treatment phase is not permitted.

Detailed rules for dose adjustments of neratinib in case of toxicity, including the dose levels to which the investigational product should be adjusted, are provided in [Appendix 2](#).

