APPENDIX 2. INVESTIGATIONAL PRODUCT DOSE ADJUSTMENT FOR TOXICITY

1. Dose adjustment levels

Recommended dose reductions for the -1 and -2 dose levels of **neratinib** and **capecitabine** are listed in [Table 3](#) in [Section 6.1.1](#) and in [Table 6](#) in [Section 6.3.1](#).

2. Toxicities Requiring Investigational Product Dose Adjustments

General Toxicities:

The guidelines for dose adjustments of **neratinib** and **capecitabine** for general toxicities due to the combination of **neratinib** plus **capecitabine** are shown in [Table A2.1](#).

Table A2.1. General Toxicities Requiring Dose Adjustment of Neratinib

NCI CTCAE v.4.0	Action
Grade 2 adverse reaction	
• 1st appearance	• Hold neratinib and capecitabine until event resolves to Grade ≤ 1 ; then resume neratinib at the starting dose level.
• 2nd appearance	• Hold neratinib and capecitabine until event resolves to Grade ≤ 1 ; then resume neratinib at 160 mg and capecitabine at 1100 mg/m ² (550 mg/m ² BID).
• 3rd appearance	• Hold neratinib and capecitabine until event resolves to Grade ≤ 1 ; then resume neratinib at 120 mg and capecitabine at 750 mg/m ² (375 mg/m ² BID).
• 4th appearance	• Discontinue neratinib and capecitabine permanently.
Grade 3 adverse reaction	
• 1st appearance	• Hold neratinib and capecitabine until event resolves to Grade ≤ 1 ; then resume neratinib at 160 mg and capecitabine at 1100 mg/m ² (550 mg/m ² BID).
• 2nd appearance	• Hold neratinib and capecitabine until event resolves to Grade ≤ 1 ; then resume neratinib at 120 mg and capecitabine at 750 mg/m ² (375 mg/m ² BID).
• 3rd appearance	• Discontinue neratinib and capecitabine permanently.
Grade 4 adverse reaction	
• 1st appearance	• Discontinue neratinib and capecitabine permanently OR if Investigator deems it to be in the patient's best interest to continue, hold neratinib and capecitabine until resolved to Grade ≤ 1 ; then resume neratinib at 120 mg and capecitabine at 750 mg/m ² (375 mg/m ² BID). • If the event occurs again despite one dose reduction, permanently discontinued neratinib .

Abbreviations: BID: twice daily; NCI CTCAE v4.0, National Cancer Institute Common Terminology for Adverse Events Version 4.0.

Gastrointestinal Toxicity:

Guidelines for adjusting doses of **neratinib** and **capecitabine** in the event of gastrointestinal toxicity diarrhea are shown in [Table A2.2](#).

Table A2.2. Gastrointestinal Toxicities Requiring Dose Adjustment of Neratinib and Capecitabine

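### Several Appendix 2 rows print a fixed neratinib dose with no limit for a patient already on less; read literally they re-escalate, against Section 6.1.1

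*Protocol*

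**What the plan says.** Protocol Section 6.1.1 sets the general rule. After a reduction, "all subsequent cycles must be administered at that dose, unless further dose reduction is required". It adds: "Dose re-escalation will only be permitted if explicitly approved in advance by the Sponsor". SAP Section 2.3.2 repeats both sentences.

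Section 6.1.1 also gives Appendix 2 its authority. It refers sites there for the detailed rules, "including the dose levels to which the investigational product should be adjusted", and states: "The dose adjustment guidelines represent the minimum set of measures the Investigator must follow".

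The Appendix 2 rows at issue are:

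- **Table A2.1, Grade 2, first appearance:** hold, "then resume neratinib at the starting dose level".
- **Table A2.1, Grade 2 second appearance and Grade 3 first appearance:** hold, "then resume neratinib at 160 mg and capecitabine at 1100" mg/m².
- **Table A2.2, row 1 (milder or shorter diarrhea):** continue neratinib at full dose.
- **Table A2.7 (hand and foot syndrome, Grades 1 to 3):** continue neratinib at the starting dose.
- **Table A2.8 (Grade 2 or 3 pancreatitis, where restart is allowed):** restart neratinib at 160 mg.

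The lead-in to Table A2.1 says that it is "for general toxicities due to the combination of" neratinib plus capecitabine. That points to metastatic patients after the second colonoscopy.

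**The concern.** Each of these rows is written as if the patient were still on 240 mg, or at least above the listed dose. Within one grade of Table A2.1 the doses only go down. The difficulty comes when a patient was reduced earlier under a different row or table and then enters one of these rows: the listed dose is now above the dose being taken.

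A site working from the row alone would raise neratinib at or just after a toxicity, without the approval that Section 6.1.1 requires. A site that also applies Section 6.1.1 would hold the lower dose. Two sites following the same protocol could therefore dose the same patient differently.

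**Working it through.** **Inputs.** Neratinib levels are 240, 200, 160 and 120 mg (Protocol Table 3; SAP 2.3.2). The starting dose level is taken as 240 mg, Table 3's recommended starting dose. Six rows of Table A2.1 print a resume dose.

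**Rule.** A row re-escalates when its listed dose exceeds the current dose. The change is listed ÷ current − 1.

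| A2.1 row | Listed (mg) | from 240 | from 200 | from 160 | from 120 |
|---|---|---|---|---|---|
| Grade 2, 1st | 240 | same | +20% | +50% | +100% |
| Grade 2, 2nd | 160 | lower | lower | same | +33% |
| Grade 2, 3rd | 120 | lower | lower | lower | same |
| Grade 3, 1st | 160 | lower | lower | same | +33% |
| Grade 3, 2nd | 120 | lower | lower | lower | same |
| Grade 4, 1st (if continued) | 120 | lower | lower | lower | same |

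The ratios are 240/200 = 1.20, 240/160 = 1.50, 240/120 = 2.00 and 160/120 = 1.33. Of 6 × 4 = 24 row-and-dose pairs, 3 + 1 + 1 = 5 raise the dose.

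**Is 120 mg a possible current dose?** Table 3 labels it "Third dose reduction", and Section 10.1 stops neratinib after more than two reductions unless the Medical Monitor agrees otherwise. Table A2.1, however, reaches 120 mg in two steps (240 to 160 to 120). The documents do not say whether reductions are counted by level or by event. If 120 mg is excluded as a current dose, 6 × 3 = 18 pairs remain and 2 raise the dose (+20% and +50%).

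**The other tables.** Taking full dose as 240 mg, A2.2 row 1 and the A2.7 rows give the same increases as the first line above. A2.8 raises the dose only from 120 mg (+33%). By contrast, A2.6 keeps neratinib at the same dose and raises no problem.

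**Can a reduced patient get there?**

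- *200 mg.* Under A2.2 row 2, Grade 3 diarrhea lasting more than 2 days, with recovery 1 to 4 weeks after the hold, drops neratinib one level, to 200 mg in Table 3. A first Grade 2 reaction under A2.1 then prints 240 mg: +20%.
- *160 mg.* A2.4 (Grade 3 ALT or bilirubin) prints a resume dose of 160 mg, and A2.3 (Grade 2 pneumonitis) a reduction to 160 mg. A first Grade 2 reaction under A2.1 then prints 240 mg: +50%.
- *Within A2.1 alone.* A first Grade 3 reaction gives 160 mg, and a first Grade 2 reaction of another kind then prints 240 mg. This route depends on appearances being counted separately by reaction and grade, which the table does not define.

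**With a cap at min(listed, current).** The five rises become min(240, 200) = 200, min(240, 160) = 160, min(240, 120) = 120 and, twice, min(160, 120) = 120. Re-escalating pairs fall to 0 of 24 and 0 of 18. For a patient on 240 mg, min(listed, 240) is the listed dose, so nothing changes.

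**The case against.** The strongest reply is that Section 6.1.1 already answers the question. Its rule is mandatory, the SAP repeats it, and because the guidelines are only a minimum, a site that stays on the lower dose arguably satisfies both texts. Appendix 2 is also not cut off from that rule: its item 1 points to Table 3 in Section 6.1.1, although only for the dose levels. The row wording reads like shorthand for an unreduced patient; an instruction to continue, as in A2.2 row 1 and A2.7, cannot sensibly mean to raise.

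Most of this stands as evidence of intent. A reader might infer that the protocol means to re-escalate after toxicity; Section 6.1.1 rules that out. It does not remove the conflict. The same section sends sites to Appendix 2 for the dose, and the row prints a different one. A2.2 shows that the drafters could condition on history: its rule for a second event asks whether neratinib has already been decreased.

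The size can also be over-read. The 5-of-24 count is a grid of wording, not a risk. No rate is given for these sequences, only 3 to 5 patients will be enrolled, and the number with metastatic disease is not stated.

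**Conclusion.** The point holds as an internal dosing conflict with a small safety consequence. In Table A2.1, three rows and 5 of 24 row-and-dose pairs re-escalate on a literal reading, or 2 of 18 if 120 mg is out of reach. A2.2 row 1, A2.7 and A2.8 share the fault, so it is not confined to A2.1. The firmest examples are +20% (200 to 240 mg, after an A2.2 reduction) and +50% (160 to 240 mg, after an A2.3 or A2.4 reduction).

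This assumes that starting dose level and full dose both mean 240 mg, and that the later reaction counts as a first Grade 2 appearance despite the earlier event. No probability is claimed.

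The point bears mainly on metastatic patients in the combination phase; only mainly, because A2.2's lead-in is not restricted to the combination. A reader might infer that the trial's results are at risk. The documents do not support that: the A2.1 combination phase follows the second colonoscopy, and neither the primary endpoint nor any statistical figure changes.

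**What to change.** Add one sentence at the head of Appendix 2, applying to all its tables:

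*Where a table gives a neratinib dose, give the listed dose or the patient's current prescribed dose, whichever is lower; re-escalation requires advance Sponsor approval per Section 6.1.1.*

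Placing it at the head is better than editing three A2.1 rows, which would leave A2.2, A2.7 and A2.8 as they are and might suggest that they are exempt. The cost is one sentence in a protocol amendment, with no new procedures or data.

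The sponsor should also consider whether the same limit should apply to capecitabine. The two A2.1 rows that resume neratinib at 160 mg also resume capecitabine at 1100 mg/m². For a patient already at 750 mg/m² under A2.6 or A2.7 that is a rise of 1100/750 − 1 = 47%, and Section 6.3.1 states no re-escalation rule for capecitabine.

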- Instruct patients to promptly report diarrhea symptoms.
- Instruct patient to record the number of stools per day and the dose of any anti-diarrheal medication taken each day (see [Section 8.5](#)).

For new onset uncomplicated Grade 1 or Grade 2 diarrhea

Dietetic measures

- Stop all lactose-containing products.
- Drink 8 to 10 large glasses of clear liquids per day (~2000 mL).
- Eat frequent small meals.
- Recommend low fat regimen enriched with bananas, rice, applesauce and toast until resolution of diarrhea.

Pharmacological treatment

- Administer loperamide: initial dose of 4 mg (2 tablets/capsules) with the first bout of diarrhea followed by 2 mg (1 tablet/capsule) every 4 hours or after every unformed stool (maximum 16 mg a day) and continue loperamide at this frequency until diarrhea-free for 12 hours.
- At any time during the study, for patients with persistent Grade 1 diarrhea on loperamide, Lomotil® (diphenoxylate hydrochloride and atropine sulfate) 1 tablet (2.5 mg) every 6 hours to 8 hours may be added (or equivalent as approved by the Sponsor).
- For 28 days of neratinib monotherapy following the second study colonoscopy procedure in patients with stage 1 to 3c breast cancer treated in the extended adjuvant setting, or during Cycle 2 in patients with mBC and beyond, for Grade 2 diarrhea (4 to 6 stools per day above baseline, despite intensive antidiarrheal therapy), consider adding octreotide (short-acting) 150 µg subcutaneously (SC) TID; or after initial dose of short-acting octreotide, if well tolerated, a single dose of octreotide LAR 20 mg intramuscularly (IM) (equivalent medication may be used with approval of the Sponsor).

For Grade 3 or Grade 4 diarrhea with complicating features (dehydration, fever, and/or Grade 3-4 neutropenia)

Dietetic measures (same as above)

Pharmacologic treatment

- Administer loperamide: initial dose of 4 mg (2 tablets/capsules) with the first bout of diarrhea followed by 2 mg (1 tablet/capsule) every 4 hours or after every unformed stool (maximum 16 mg a day) and continue loperamide at this frequency until diarrhea-free for

12 hours. Then titrate the amount of loperamide used to keep diarrhea controlled (<4 stools/day).

- Administer octreotide [100-150 µg SC BID or intravenously (IV) (25-50 µg/h) if dehydration is severe, with dose escalation up to 500 µg SC TID].
- Use IV fluids as appropriate.

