NCI CTCAE V4.0	Action

 Grade 1 Diarrhea [Increase of <4 stools per day over baseline; mild increase in ostomy output compared to baseline.] OR Grade 2 Diarrhea [Increase of 4-6 stools per day over baseline; moderate increase in ostomy output compared to baseline;] lasting <5 days OR Grade 3 Diarrhea [Increase of ≥ 7 stools per day over baseline; incontinence; hospitalization indicated; severe increase in ostomy output compared to baseline limiting self-care activities of daily living (ADL)] lasting ≤ 2 days 
 Persisting and intolerable Grade 2 Diarrhea lasting ≥ 5 days despite being treated with optimal medical therapy, or associated with fever, dehydration, or Grade 3-4 neutropenia OR Grade 3 Diarrhea lasting > 2 days despite being treated with optimal medical therapy, or associated with fever, dehydration, or Grade 3-4 neutropenia OR Any Grade 4 diarrhea [Life-threatening consequences; urgent intervention indicated] 	
 Adjust anti-diarrheal treatment, as per the guidelines for management of diarrhea at the first onset of diarrhea (refer to Section 6.2 and Section 7.2). Continue neratinib and capecitabine at full dose. Instruct patient to follow dietetic recommendations in the guidelines for management of diarrhea (refer to Section 7.2). Fluid intake of ~ 2L should be maintained to avoid dehydration. Once the event resolved to \leq Grade 1 or baseline, start loperamide 4 mg with each subsequent neratinib administration. 
 Adjust anti-diarrheal treatment, as per the guidelines for management of diarrhea at the first onset of diarrhea (refer to Section 6.2 and Section 7.2). Hold neratinib and capecitabine until recovery to \leq Grade 1 or baseline. Instruct patient to follow dietetic recommendations of the guidelines for management of diarrhea. Fluid intake of ~ 2L should be maintained, intravenously if needed. If recovery occurs: 
 ≤ 1 week after withholding treatment, resume same dose of neratinib and capecitabine. Within 1-4 weeks after withholding treatment, reduce neratinib dose to the next lower dose level and maintain the same dose of capecitabine. If event occurs a 2nd time and the neratinib dose has not already been decreased, reduce neratinib dose to the next lower dose level and maintain the same dose of capecitabine. If neratinib dose has already been reduced, then reduce the dose of capecitabine to 1100 mg/m^2^a (550 mg/m^2 BID) (maintain same dose of neratinib) If subsequent events occur, reduce the dose of neratinib or capecitabine to the next lower dose level in an alternate fashion (i.e., reduce capecitabine to 750 mg/m^2 (375 mg/m^2 BID) if neratinib was previously reduced, or reduce neratinib to 120 mg if capecitabine was previously reduced.. Once the event resolved to \leq Grade 1 or baseline, start loperamide 4 mg with each subsequent neratinib administration.

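### Table A2.2 gives opposite dosing instructions for Grade 3 diarrhea of 2 days or less with complications, and no text says which row prevails

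*Protocol*

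**What the plan says.** Section 6.1.1 refers neratinib dose changes for toxicity to Appendix 2, where Table A2.2 deals with diarrhea in two rows.

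- **Row 1** covers Grade 1, Grade 2 lasting under 5 days, and Grade 3 lasting 2 days or less. None of these criteria mentions complications. The action is "Continue neratinib and capecitabine at full dose", with the advice "Fluid intake of ~ 2L should be maintained to avoid dehydration".
- **Row 2** covers a Grade 2 category that opens "Persisting and intolerable Grade 2 Diarrhea", any Grade 4 event, and "Grade 3 Diarrhea lasting > 2 days despite being treated with optimal medical therapy, or associated with fever, dehydration, or Grade 3-4 neutropenia". The action is "Hold neratinib and capecitabine until recovery to" Grade 1 or lower, or baseline, with the advice "Fluid intake of ~ 2L should be maintained, intravenously if needed".

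No footnote or sentence ranks the rows. Section 6.1.1 adds: "The dose adjustment guidelines represent the minimum set of measures the Investigator must follow". It also lets the investigator do more on medical judgment.

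**The concern.** Section 7.2 names diarrhea as neratinib's major dose-limiting toxicity, and Table A2.2 is its dosing rule. A patient on the first day of Grade 3 diarrhea with fever fits the row that continues treatment and, read naturally, the row that stops it. One site could keep dosing while another holds, and each could point to the table. At stake are the safety of a febrile, dehydrated or neutropenic patient and uniform dosing across about two centers. In Cycle 1 only neratinib is affected, because capecitabine starts after the second colonoscopy.

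**Working it through.** The plan states no figure on this point, so the check is a reading of the text. A complication here means fever, dehydration or Grade 3-4 neutropenia.

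**Step 1. Two readings of row 2 for Grade 3.** Reading A treats the complication clause as a separate trigger, parallel to the duration clause. Reading B lets the limit of more than 2 days govern both.

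| Grade 3 event | Reading A | Reading B |
|---|---|---|
| 2 days or less, no complication | continue | continue |
| 2 days or less, complication | **continue and hold** | **continue** |
| More than 2 days despite optimal therapy, no complication | hold | hold |
| More than 2 days despite optimal therapy, complication | hold | hold |

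Under A, 1 of 4 cells conflicts. Under B, 0 of 4 do, but the same cell becomes full dosing through complicated Grade 3 diarrhea. Reading A is the more natural: the two clauses are joined by a simple alternative, and Section 7.2 treats complications as a category of their own with no duration limit.

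**Step 2. When the conflict arises.** It covers days 1 and 2 of an episode. Dosing is daily, and every Grade 3 episode passes through those days. A complication present then meets both rows when the next dose is decided, however long the episode finally lasts.

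**Step 3. Search for a tie-breaker.**

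- Section 6.1.1 makes the guidelines a minimum. That permits a hold but ranks no rows.
- Section 7.2 has one heading "For new onset uncomplicated Grade 1 or Grade 2 diarrhea" and another for complicated Grade 3-4 diarrhea. Both cover diet, drugs and supportive care, not whether to continue neratinib.
- Section 7.2 closes by saying that significant, unresponsive diarrhea may need interruption or a lower dose. This does concern dosing, but it is permissive and limited to unresponsive cases.
- Section 7.2 offers advice from the Sponsor or Medical Monitor where there is concern. A site reading only row 1 may have none.
- The fluid instructions suggest that row 1 patients are not yet dehydrated. They do not address fever or neutropenia.
- Table A2.1 holds both drugs for Grade 2-3 reactions, and Table A2.6 continues neratinib through Grade 3-4 hematologic toxicity. Both are introduced as applying to toxicity of the neratinib-capecitabine combination, so neither settles the question, least of all in Cycle 1.

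**Step 4. Grade 2.** Row 1 takes Grade 2 on days 1-4. If row 2's complication clause stands alone, complicated Grade 2 on those 4 days meets both rows. If the words on persistence and intolerability govern that clause too, at most the intolerable cases do. The text does not decide this.

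**Step 5. Frequency.** The documents give no rate for short complicated Grade 3 events. Section 2.3.3 says that severe or serious complications were rare in Study 3004, which had no mandated prophylaxis. Hospitalization for diarrhea was 20/1408 = 1.4% there (Table 1) and 2/137 = 1.5% in Study 6201 (Table 2), but that is a different event over the whole treatment period. No probability of the conflict can be derived from it.

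**The case against.** The strongest reply is that the table nearly resolves itself. On Reading A, longer Grade 3 events on optimal therapy are already held, so the complication clause does almost all its work on short events. Letting row 1 prevail would nearly empty it. And if both rows state minimum measures, continuing breaches row 2, while holding can be defended as an additional measure over row 1. With the Section 7.2 material, this makes holding the better inference and lowers the chance that sites would diverge. That stands, and it reduces the weight of the point. It remains an inference: a site that stops at row 1 finds a plain instruction to continue.

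The reply is also right on two stronger readings that a reader might infer.

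- *Table A2.6 contradicts row 2 and needs an override.* The documents do not support this. Table A2.6 addresses hematologic abnormalities under the combination. Row 2 addresses diarrhea accompanied by neutropenia and can govern as the more specific rule.
- *All complicated Grade 2 diarrhea should be held.* For short, tolerable cases that may be a new clinical threshold rather than the repair of a contradiction.

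**Conclusion.** The contradiction holds for Grade 3 diarrhea of 2 days or less with fever, dehydration or Grade 3-4 neutropenia. It rests on reading the complication clause as a separate trigger. On the other reading there is no contradiction, but the table then prescribes full dosing in just those patients, so the wording needs repair either way. Grade 4 events, and Grade 3 lasting more than 2 days despite optimal therapy, are clearly held. The Grade 2 overlap is possible but uncertain.

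The weight is modest: the frequency is unknown, 3-5 patients will be enrolled, and the surrounding text favours holding. A reader might infer that inconsistent holds would distort the biopsy comparison. The documents show no such effect, and SAP Section 6.7.1 lists an indicator of dose withheld for adverse events for each patient. The case for the change is patient safety and uniform dosing.

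**What to change.** Make three edits to Table A2.2.

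1. In row 1, limit the Grade 3 criterion to events of 2 days or less that are free of fever, dehydration and Grade 3-4 neutropenia.
2. In row 2, separate the two Grade 3 triggers: more than 2 days despite optimal medical therapy; or any duration when accompanied by fever, dehydration or Grade 3-4 neutropenia.
3. Add one sentence: *if an event meets both rows, row 2 applies.*

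The third edit also settles Grade 2 wherever an overlap exists, without setting a new threshold where none does. The edits do not make the table exhaustive. For example, uncomplicated Grade 3 beyond 2 days without optimal therapy would still fall in neither row.

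The cost is a few words by amendment, with no new procedures or data, and probably a few more short holds. Row 2 resumes the same dose if recovery takes a week or less. Recovery within 1-4 weeks lowers the neratinib dose one level, and so does a second event if that dose has not already been reduced.

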NOTE; patients with mBC cannot be exposed to capecitabine until after completion of the second study colonoscopy procedure.

In extended adjuvant patients with stage 1 to 3c breast cancer, patients will return to the clinic approximately every 3 months for safety assessments. End of Treatment (EOT) visit is planned on upon completion of 1 year of treatment, followed by Safety Follow-up Visit 28 days after the last dose of neratinib.

In patients with mBC, clinic visits during the active treatment phase are planned on Day 1 of Cycle 1, Cycle 2, and each subsequent cycle. Treatment discontinuation visit is planned 0-3 days after the last dose, followed by a Safety Follow-up Visit 28 days after the last dose of neratinib.

Assessments required throughout the study are summarized in the Schedule of Study Procedures ([Appendix 1](#)).

Patients may be discontinued from investigational product or from the study, as described in [Section 10](#) and [Section 11](#).

The primary endpoint of the study is change from baseline in pathological findings in colon biopsies after the first 28 days of neratinib. The secondary endpoint is the incidence and severity of diarrhea during the first 28-day cycle.

The study will end when all patients have been followed-up for 28 days after the last dose of neratinib.

Approximately 3-5 patients will be enrolled at approximately 2 centers.

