- Consider prophylactic antibiotics as needed (eg, fluoroquinolones) especially if diarrhea is persistent beyond 24 hours or there is fever or Grade 3-4 neutropenia.

The Investigator or designee should contact the Sponsor or the Medical Monitor for advice if at any time there is a concern for the appropriate course of action for the management of diarrhea.

Stool cultures should be done to exclude infectious causes of Grade 3 or Grade 4 diarrhea or diarrhea of any grade with complicating features (dehydration, fever, and/or Grade 3 or Grade 4 neutropenia) per the Investigator's discretion. Results from occult blood, fecal leukocyte stain, *Clostridium difficile*, *Campylobacter*, *Salmonella*, and *Shigella* testing, when performed, should be reported using the appropriate CRF.

Patients with significant diarrhea who are unresponsive to medical treatment may require treatment interruption or dose reduction.

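### Table A2.2's repeat-event diarrhea rules presuppose capecitabine and cannot be carried out as written for patients on neratinib alone

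*Protocol*

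**What the plan says.** Protocol Section 6.1.1 sends all neratinib dose changes to Appendix 2 and gives those rules force: "The dose adjustment guidelines represent the minimum set of measures the Investigator must follow". The sentence after it allows further measures at the investigator's judgment. Table A2.2 is the only dose-adjustment table for diarrhea.

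The lower row of Table A2.2 covers three kinds of event: Grade 2 that persists for 5 days or more or is complicated, Grade 3 that lasts more than 2 days or is complicated, and any Grade 4. Treatment is held at each such event. The row then gives:

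- **Recovery time.** Recovery within 1 week returns the patient to the same doses. Recovery in 1 to 4 weeks lowers neratinib one level and leaves capecitabine alone.
- **Second event.** Neratinib is lowered if it has not been lowered before. Otherwise: "If neratinib dose has already been reduced, then reduce the dose of capecitabine to 1100" mg/m², with the instruction to "maintain same dose of neratinib".
- **Later events.** "If subsequent events occur, reduce the dose of neratinib or capecitabine to the next lower dose level in an alternate fashion". The two branches spelled out are capecitabine to 750 mg/m² if neratinib was lowered before, "or reduce neratinib to 120 mg if capecitabine was previously reduced".

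Under Section 4.1, both groups take neratinib alone in the 28-day Cycle 1, and stage 1 to 3c patients continue on it alone for up to 1 year. The same section states that "patients with mBC cannot be exposed to capecitabine until after completion of the second study colonoscopy procedure".

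Table 3 lists reductions from 240 mg to 200, 160 and 120 mg, the last labelled "Third dose reduction". Section 10.1 requires discontinuation if more than 2 neratinib reductions are needed, unless otherwise agreed with the Medical Monitor.

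**The concern.** The repeat-event bullets were written for two drugs and apply, without adaptation, to patients taking one. An already-reduced monotherapy patient with another qualifying event is told to lower a drug that is not being taken and to keep the one that is. The later neratinib step that is spelled out rests on a condition that patient can never meet.

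The first stake is conduct and safety. Section 7.2 calls diarrhea the major dose-limiting toxicity, and two investigators could follow the same row to different doses.

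The second stake is the data. The gap opens only after a first reduction, so the SAP's time to first dose reduction (Section 6.9.1) is not affected. What can move is the lowest reduction level, cumulative dose and dose intensity (SAP Section 6.7.1), the number of interruptions, and the diarrhea that follows. With 3 to 5 patients at about 2 centers, one patient handled differently would be visible in these results.

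**Working it through.** The plan gives no figure to reproduce here; Section 12.5 sets the sample size by feasibility. The check is a literal trace of the row, followed by two scale calculations.

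**1. Trace after a first neratinib reduction at event 1 (recovery in 1 to 4 weeks)**

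| Event | Neratinib plus capecitabine | Neratinib alone |
|---|---|---|
| 2nd | Capecitabine to 1100 mg/m², neratinib kept | Capecitabine step has no object, neratinib kept |
| 3rd | Neratinib to 120 mg (capecitabine was lowered last) | Only the capecitabine branch is met; not executable |
| 4th | Capecitabine to 750 mg/m² | Same as 3rd |

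If event 1 resolves within a week instead, neratinib is first lowered at event 2. The monotherapy patient then meets the same block at event 3. On either route, the second-event bullet and the spelled-out alternation give 0 executable neratinib cuts after the first. Table 3 lists three reductions, and Section 10.1 tolerates two.

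**2. Competing text in the same row, for a monotherapy patient already reduced**

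| Situation | Text that keeps neratinib | Text that lowers neratinib |
|---|---|---|
| 2nd event, recovery within 1 week | Recovery bullet; second-event bullet | None in the row |
| 2nd event, recovery in 1 to 4 weeks | Second-event bullet | Recovery bullet |
| Later event, recovery within 1 week | Recovery bullet; spelled-out branches | Opening words of the later-events bullet |
| Later event, recovery in 1 to 4 weeks | Spelled-out branches | Recovery bullet; opening words of the later-events bullet |

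The recovery bullet is not limited to a first event. In three of the four situations the row supports both actions.

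**3. Room for the problem in Cycle 1**

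Assume the first qualifying event triggers a hold on Day d and recovery takes just over 1 week, so dosing resumes at the reduced level on Day d + 8. Days left in the cycle = 28 − (d + 8) + 1.

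- d = 1: resume Day 9, 20 days left.
- d = 5: resume Day 13, 16 days left.

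A second qualifying event would have to fall in those 16 to 20 days. That is possible, but the window is narrow. Stage 1 to 3c patients carry the ambiguity for the rest of the year.

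**4. Scale**

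The gap needs a neratinib reduction and then a further qualifying event. The documents give a rate only for the first part. P(at least one of n) = 1 − (1 − p)ⁿ.

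- Study 6201, loperamide cohort (Table 2), p = 11/137 = 0.080: n = 3 gives 1 − 0.920³ = 0.22; n = 5 gives 1 − 0.920⁵ = 0.34.
- Study 3004, no mandated prophylaxis (Table 1), p = 372/1408 = 0.264: n = 3 gives 0.60; n = 5 gives 0.78.

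Study 6201 is the closer context because this trial mandates loperamide. Both are rates over the full treatment period, and both are upper bounds on reaching the gap at the stated p, because the further event is not yet counted.

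**The case against.** The strongest reply is that no patient is trapped. Neratinib is held at every qualifying event. The recovery bullet can lower it again, and the later-events bullet opens by naming either drug. Section 6.1.1 allows measures beyond the minimum, Section 7.2 gives a route to the Sponsor or Medical Monitor, and Section 10.1 lists toxicity as a ground for stopping. Results are presented mainly as listings, with each patient's neratinib exposure and reductions shown, so any difference in handling could be seen.

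Most of this stands, and it limits the point. A reader might infer that monotherapy patients have no further reduction step at all; the recovery bullet and the opening of the later-events bullet show otherwise. A reader might also infer that neratinib stays fixed for everyone from the second event; for combination patients the trace has it falling at the third. Section 7.2's remark that "Patients with significant diarrhea who are unresponsive to medical treatment may require treatment interruption or dose reduction" is permissive and is met by a hold, so it is not a firm contradiction. Table 3 lists available levels and does not require each to be used for diarrhea.

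What the reply does not do is make the row give one answer. Latitude under Section 6.1.1 permits a further cut but leaves it to each investigator, against an explicit instruction to keep the dose. Holding and contact routes do not settle the dose at which the patient resumes.

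**Conclusion.** The point holds as an internal conflict that should be fixed. Read literally, the second-event and alternating rules cannot be carried out for an already-reduced patient on neratinib alone, and neighbouring text supports the opposite action.

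The number of patients affected is unknown. The 22% to 34% figure is the chance that at least one of 3 to 5 patients has any diarrhea dose reduction. It assumes independent patients and that Study 6201's rate carries over. The chance of a further qualifying event is smaller by a factor the documents do not give.

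It is tempting to use Study 6201's 42/137 with Grade 3 diarrhea, which gives 67% for 3 patients and 84% for 5. The arithmetic is right, but it counts any Grade 3 diarrhea over the whole treatment period. Uncomplicated Grade 3 lasting 2 days or less stays at full dose under Table A2.2, and the gap needs a repeat event after a reduction. Those figures do not measure it.

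An effect on the biopsy endpoint or on Cycle 1 diarrhea is possible but unlikely, given the short window. The main exposure is in stage 1 to 3c patients after Cycle 1.

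**What to change.** Reconcile Table A2.2 with Table 3 and Section 10.1, and those two with each other: three listed reductions stand against discontinuation beyond two, unless otherwise agreed with the Medical Monitor. In Table A2.2, state the recurrence bullets twice:

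- for neratinib alone (all patients in Cycle 1 and until the second colonoscopy, and stage 1 to 3c patients throughout), with each step referring only to neratinib;
- for neratinib plus capecitabine.

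State also whether the recovery-time bullet applies at repeat events and, if so, which bullet governs when it and the recurrence bullet disagree. The sponsor decides the steps; no dose or clinical rule is proposed here.

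The cost is a protocol amendment to the wording of one appendix table, with matching edits to Table 3 or Section 10.1. SAP Section 2.3.2 repeats the neratinib levels and would need to follow any change to Table 3. No new data or procedures are needed.
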